The present study will recruit 25 male adolescents between the ages of 13 and 17 years. Participants will be recruited via advertisements in the community (e.g., grocery stores, fitness centers, restaurants), at CHEO, and through word of mouth. Volunteers will be excluded for any of the following reasons: smoking, unstable body weight (± 4 kg) during the 3 months preceding testing, excessive alcohol intake (>15 drinks/week), celiac disease, metabolic disease (e.g., thyroid disease, heart disease, diabetes), medication use that could interfere with the outcome variables, highly restrained eating behavior (score of ≥ 12 for cognitive dietary restraint on the Three-Factor Eating Questionnaire), irregular sleeping pattern (e.g., shift work or working overnight shifts), and inability to comply with the protocol. Following a phone call with the potential participant to confirm eligibility and explain the study, consent forms will be mailed and

will need to be returned to us in the pre-paid envelope provided before any testing can begin. Participants who are capable of consenting will be asked to do so on their own behalf; otherwise, written informed parental consent and child assent will be obtained. Ethical approval will be obtained from the Children's Hospital of Eastern Ontario Research Ethics Boards. Participants will receive \$30 per condition for their participation in the study (\$120 total).

Overview of the Study Protocol

Preliminary Visit

The participants will attend one baseline session and three experimental sessions, each separated by at least one week. All sessions will begin at 07:30, and the participants will be instructed to fast and abstain from structured exercise for 12 hours before each visit. The preliminary visit will include measurements related to anthropometry (body weight, height, waist circumference), resting metabolic rate and cardiorespiratory fitness (VO_2 peak). Participants will also complete questionnaires in order to better characterize them. During this initial visit, participants will be asked to identify any food allergies or intolerances that might impact the standardized breakfast and buffet meals provided during the experimental sessions.

Experimental Sessions

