A standardized breakfast will be given to the participants at 08:00, consisting of 2 pieces of whole-wheat bread (78 g, 837 kJ; D'Italiano), peanut butter (18 g, 452 kJ; Kraft Smooth Peanut Butter), raspberry jam (16 mL, 218 kJ; Kraft Pure Raspberry), cheddar cheese (21 g, 335 kJ; Kraft Cracker Barrel Marble), and orange juice (200 mL, 418 kJ; Minute Maid 100% Orange Juice). Participants will eat alone in a room with no distractions, and will need to consume the entire breakfast within 15 min. Participants with food intolerances will have individual food items replaced; however, they will receive an identical breakfast at each of the three visits.

Ad libitum lunch

Spontaneous food intake, including liquids, will be assessed by using an *ad libitum* food menu immediately after each experimental condition, which will allow us to assess both total energy intake and macronutrient preference (12). The food menu contains a variety of meal-type foods (both hot and cold), beverages, and snacks differing in macronutrient composition (74 items in total). The foods will be offered in large amounts, and the participants will be instructed to eat *ad libitum*, alone, in a room without distractions, with no restrictions on the amount to be consumed. The participants will be given 30 min for this meal, and all foods will be measured to the nearest 0.1 g before and after ingestion. *Ad libitum* energy intake will be measured by a food technician using calculations performed on the amount of the meal consumed. This type of food menu, which has a high appreciation of food items on the menu, has been shown to produce a reliable measure of energy intake inside the laboratory in both adults and adolescents (12, 13).

Appetite Sensations

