The procedures of the proposed study have been chosen to minimize the burden and risk posed to the personal safety of study participants. Participants with food allergies will be excluded from the study because many food items we serve have been associated with allergic reactions (e.g. peanuts, wheat, etc.). The foods are prepared by our research coordinators in our experimental kitchen and we adhere to the Canadian food safety guidelines for families. The aerobic fitness test will be performed under the supervision of a certified exercise physiologist, with CPR and first aid certifications, and who is specifically trained to screen-out participants prior to the test, terminate the test in the face of specific contraindications, and manage any adverse events should they occur. A proper warm-up and cool-down will also be conducted to prevent injuries. In the unlikely event that participants experience an injury, medical or other crisis (e.g. chest pain, heart attack, psychotic episode, panic attack, etc) during the fitness test, a safety protocol is in place in the HALO laboratory and the hospital emergency response team will be contacted immediately. Staff will immediately accompany unstable participants to the emergency room at CHEO, and stay with them until they are assessed. Parents will be contacted and informed of this emergency for participants. Finally, if participants feel uncomfortable with some of the questions being asked in the questionnaires, they may choose not to answer a question.

CONFIDENTIALITY AND PRIVACY

Personal information will be kept strictly confidential except as required or permitted by law. The data produced from this study will be stored in a locked filing cabinet. Only members of the research team will have access to the data. Following completion of the research study the data will be kept for 7 years after the last publication of this study. They will then be destroyed. Participants will not be identified in any publication or presentation of this study.

STATISTICAL CONSIDERATIONS

Outcome Measures

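### Does leaving food allergy out of the exclusion list let an allergic boy into the study meals?

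*Combined protocol and SAP*

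**What the plan says.** Four parts of the combined protocol and SAP bear on food allergy.

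- **Participants.** The eligibility paragraph begins "Volunteers will be excluded for any of the following reasons: smoking, unstable body weight" and ends with "inability to comply with the protocol". Eligibility is checked by telephone before consent ("Following a phone call with the potential participant to confirm eligibility and explain the study"), and the consent forms "will need to be returned to us in the pre-paid envelope provided before any testing can begin".
- **Preliminary Visit.** Of all visits it is said that "the participants will be instructed to fast and abstain from structured exercise for 12 hours before each visit". At this first one, "participants will be asked to identify any food allergies or intolerances that might impact the standardized breakfast and buffet meals provided during the experimental sessions".
- **Breakfast.** The meal is fixed, "consisting of 2 pieces of whole-wheat bread" together with peanut butter, jam, cheddar cheese and orange juice, and all of it must be eaten. Individual items are swapped for boys with intolerances. Allergies are not mentioned here.
- **Potential Risks.** The rule is plain and gives its reason: "Participants with food allergies will be excluded from the study because many food items we serve have been associated with allergic reactions". Peanuts and wheat are named as examples.

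**The concern.** The exclusion list is written as a complete list, with no wording to show that it is only illustrative. It does include celiac disease, so food-related conditions evidently belong in it. A reader would expect food allergy there too.

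The visit question adds to the doubt. It puts allergies and intolerances together and asks how they would affect the meals, which reads more like menu planning than an eligibility check. The restraint criterion makes a useful contrast: it is in the exclusion list and is repeated under Questionnaires, where it is assessed. Allergy has neither link.

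What would be at stake is the safety of minors. Someone screening from the list alone could pass a boy whom Potential Risks excludes, and his later answer at the visit could be treated as a request for a different breakfast. If allergy first came up at that visit, he would also have consented and fasted for nothing.

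The Budget section raises a related doubt. It costs breakfast for four sessions, while the Breakfast section speaks of three visits. If a breakfast were served at the preliminary visit, nothing says the allergy question comes before it.

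**Working it through.** No formula applies to the main point. The check is to set the sections side by side and follow an allergic boy through the plan as written.

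**1. The list.** The reasons under Participants are smoking, unstable weight, excessive alcohol, celiac disease, metabolic disease, interfering medication, high dietary restraint, irregular sleep and inability to comply. That is 9 reasons, and none names food allergy. The omission is real.

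**2. The telephone call.** Its questions are not itemised, so allergy may or may not be raised. A boy who learns what the breakfast contains and says he cannot eat it could be caught by the inability-to-comply ground, but this is not certain. Assume the worst case, in which he passes.

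**3. The preliminary visit.** Every boy is asked about food allergies and intolerances. The allergic boy is identified here at the latest, if he answers accurately.

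**4. The consequence.**

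| Answer at the visit | Consequence | Where stated |
|---|---|---|
| Food allergy | Excluded from the study | Potential Risks |
| Food intolerance | Breakfast items replaced, same breakfast at each of the three visits | Breakfast |

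The two rows do not conflict. No section offers replacement food to a boy with an allergy, and no section keeps him in.

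**5. Timing of food.** The described meals, breakfast and ad libitum lunch, belong to the experimental sessions, and the visit question itself places them there. Sessions are separated by at least one week. Exclusion in step 4 therefore comes before any described meal.

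**6. Exposure if step 4 failed.** Of the 5 standard breakfast items, 2 (bread and peanut butter) contain the allergens that Potential Risks names, and the meal is given at 3 sessions. The lunch menu has 74 items. These figures show why the rule exists. They do not measure how likely it is to be missed, and the document gives nothing from which that could be estimated.

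**7. The breakfast count.**

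- Budgeted: 25 × 4 = 100 breakfasts, and 100 × $6 = $600, which matches the budget line.
- Described: 25 × 3 = 75 breakfasts, and 75 × $6 = $450.
- Difference: 25 breakfasts, or $150.

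The mismatch is genuine, but no section describes a breakfast at the preliminary visit or what it would contain. It may be a budgeting slip. It measures an inconsistency in the costing, not an allergy risk.

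**8. Statistical consequence.** The intake and expenditure outcomes are measured at the experimental sessions and over the rest of those days. A boy excluded at the preliminary visit contributes no such data. The sample-size assumptions (100 kcal difference, SD 200 kcal, 25 participants) and the mixed model do not involve this criterion.

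**The case for a change.** The strongest reply is that a safety rule should not depend on staff remembering another section. For food, the only safeguards the protocol describes are this exclusion and adherence to food safety guidelines; the emergency procedure is described for events during the fitness test. The exclusion is thus the main stated protection against an allergic reaction in minors, it is absent from the list against which eligibility would be confirmed, and adding it would cost almost nothing.

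Part of this stands. The list is incomplete, the visit question should ideally point to the rule, and someone using only the list could miss the exclusion until the preliminary visit.

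The harmful outcome needs more than that. Staff would have to ask the allergy question as instructed, receive a positive answer, disregard an unconditional exclusion, and stretch a replacement provision written for intolerances to cover allergies. The omission makes late detection possible; it does not make inclusion the result of following the plan.

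The complaint about timing is weaker. Restraint is also checked by questionnaire at the preliminary visit, after consent and a fast, so settling some eligibility questions there is how this study works. Asking about allergy on the call would spare a boy a wasted visit, which is a convenience. The argument from the fourth breakfast depends on a meal that only a budget line hints at.

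**Conclusion.** The concern is accurate about the text but does not call for a change to the plan. Food allergy is missing from the 9 listed reasons and the visit question carries no cross-reference. Even so, the question, the exclusion and the limited replacement provision fit together, and they act before any meal the document describes. This is a gap in documentation that staff with the full protocol would fill in the one way it allows. Naming allergy in the list and making the breakfast count agree with the budget would be tidy, but neither would alter who is eligible or what is analysed.

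The conclusion rests on three assumptions: the allergy question is asked of every boy as stated, staff apply the Potential Risks rule to the answers, and no food is served at the preliminary visit before the question. The third cannot be fully confirmed, because the 25 extra budgeted breakfasts are unexplained. Consent pages are not in the copy reviewed, so what families are told about allergens is unknown. The number of boys affected cannot be derived, and no effect on power or analysis is shown.

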For each condition, the participants will be instructed to complete 9 VAS for their sensations of hunger, satiety, prospective food consumption, fullness, and desire to eat something sweet, salty, or rich in fat. They will also rate their opinion on the general appreciation of the meal and on the overall satisfaction/enjoyment of the experimental conditions, from “extremely boring” to “extremely pleasant”. The VAS is a line (100 mm in length) with statements anchored at each end expressing the most positive and most negative rating of the participants’ appetite sensations. The VAS have been shown to be both reproducible and valid for measurement of appetite sensations in a laboratory setting (14). The VAS will be completed during each experimental condition: at fasting (07:45), before the experimental condition (10:25), immediately after the experimental condition (11:05), and immediately after the *ad libitum* lunch.

Dietary Record

All participants will be instructed to complete a dietary record (15), with help from the parents, after each experimental condition to evaluate the degree of potential compensation in food intake for the remainder of the day. Participants will be instructed on how to complete the dietary record and on how to measure quantities of ingested foods. The food records will be reviewed with each participant upon their return to improve the validity of the information provided. Mean energy and macronutrient intakes will be calculated by using the Food Processor SQL software (version 9.6.2; ESHA Research).

Resting Metabolic Rate and Cardiorespiratory Fitness Measurements

Resting metabolic rate (RMR) will be measured during the preliminary visit by indirect calorimetry (Vmax 229 series metabolic cart; SensorMedics). RMR will be measured for 30 min after a 30-min rest period and a 12-h overnight fast. The first and last 5 min will be excluded from the calculations; thus, minutes 6-25 will be used in the calculation. Mean RMR will be calculated by using the Weir equation (16). VO_2 peak will be measured using the same metabolic cart and using the Dubowy graded treadmill protocol (17). Exercise sessions on the treadmill will be set at 60% of VO_2 peak (moderate-intensity physical activity).

Perceived Exertion

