Ratings of perceived exertion (RPE) will be used to quantify participants' perceived exertion during the experimental conditions by using the OMNI scale of perceived exertion. The scale ranges from 0 (extremely easy) to 10 (extremely hard) and has been previously validated in the pediatric population (18). Participants may find the exercise session easier to perform with the use of a stimulus (e.g., music or TV program). It is also possible that the RPE may influence post-exercise energy compensation. Participants will rate their RPE at every 5 min during the conditions and the area under the curve (AUC) will be calculated using the trapezoid method.

Physical Activity Energy Expenditure Compensation

Changes in physical activity after each condition will be assessed by using an Actical accelerometer (Philips Respironics). The accelerometer, on an elastic belt, will be positioned on the right iliac crest in midaxillary position immediately on arrival at the laboratory (07:30) and worn until bedtime. The Actical measures and records time-stamped acceleration in all directions (omni-directional), and the digitized values are summed over a user-specified interval of 1 minute. The Actical has been validated to measure physical activity in children and adolescents (19) and has better instrument reliability than other accelerometer models (20). Accelerometry data will undergo standardized quality control and data reduction procedures, as previously reported (21). Physical activity energy expenditure (PAEE) will be determined from the Actical by using validated equations (19).

Questionnaires

To better characterize the adolescents, some questionnaires will be administered during the preliminary visit. The 51-item Three-Factor Eating Questionnaire (22) will be used to

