The primary outcome measure will be post-exercise energy compensation. The food intake outcome will be assessed by using an *ad libitum* test meal immediately after the conditions and a dietary record for the remainder of the day. The energy expenditure outcome will be assessed by using an Actical accelerometer until bedtime. Total energy expenditure (TEE) will be calculated by using the following formula: $TEE = (PAEE \text{ from the Actical} + RMR) \times 1.11$ (28) where the thermic effect of food is fixed at 10% of TEE. The secondary outcome measures will include appetite sensations (VAS) and the RPE (OMNI scale).

Sample Size Calculation

It is estimated that a sample size of 25 participants will provide 90% power at 5% level of significance (two-sided) to detect a minimal group difference of 100 kcal in energy intake and expenditure, assuming a standard deviation of 200 kcal. This is based on previous studies by our group, using a similar crossover design, that compared active video game play with passive video game play in adolescents (29, 30). We used a conservative SD estimate because large variability is generally observed for energy intake (especially with the use of dietary records) and to increase the likelihood of detecting a significant difference between conditions.

Statistical Analysis

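### Does the unstated period for resting metabolic rate in the TEE formula let bedtime differences contaminate the expenditure contrast?

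*Combined protocol and SAP*

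**What the plan says.** Under Statistical Considerations, Outcome Measures, the primary outcome is post-exercise energy compensation. For its expenditure side the text reads "The energy expenditure outcome will be assessed by using an Actical accelerometer until bedtime". The next sentence begins "Total energy expenditure (TEE) will be calculated by using the following formula", and the formula is TEE = (PAEE + RMR) × 1.11, with the thermic effect of food set at 10% of TEE. No period is attached to RMR.

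The section on resting metabolic rate and cardiorespiratory fitness says "Resting metabolic rate (RMR) will be measured during the preliminary visit by indirect calorimetry", so each participant has one RMR value for all three conditions. The section on physical activity energy expenditure compensation says "Changes in physical activity after each condition will be assessed by using an Actical accelerometer" and "Physical activity energy expenditure (PAEE) will be determined from the Actical by using validated equations"; the device goes on at 07:30 and comes off at bedtime.

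The Preliminary Visit section fixes the start of the day ("All sessions will begin at 07:30") and the spacing of visits ("each separated by at least one week"), but neither the bedtime nor the day of the week. The Sample Size Calculation is framed as power "to detect a minimal group difference of 100 kcal in energy intake and expenditure", with a standard deviation of 200 kcal.

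**The concern.** RMR is a rate. To enter a sum in kcal it must be multiplied by a duration, and the plan does not give one. Bedtime is the only end point the text names for expenditure, so a reader could count RMR over the same window as the accelerometer. That window would differ between a participant's sessions, and RMR would no longer cancel from the comparison of conditions. Resting expenditure goes on after bedtime, so an early night would register as lower expenditure, which is the direction the trial calls compensation.

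At stake would be the precision of the expenditure contrast and, if a condition itself shifted bedtime, its validity. Randomising the order of conditions does not exclude the second possibility, because bedtime comes after the exercise session and could be affected by it. The text also leaves open whether PAEE or TEE is tested, so in principle the choice could be made after the data are seen.

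**Working it through.** **Inputs from the documents:** multiplier 1.11; thermic effect 10% of TEE; n = 25; two-sided 5%; 90% power; difference 100 kcal; SD 200 kcal; RMR measured once.

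**Assumed, because the documents give no value:** RMR 1400 to 2000 kcal/day; within-person bedtime SD 0.5 to 1.0 h, independent of other variation.

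**Step 1, the plan's own figure.** TEE = PAEE + RMR + 0.10 × TEE gives a multiplier of 1/(1 − 0.10) = 1.111, which agrees with 1.11.

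**Step 2, RMR over a fixed period.** For one participant under conditions i and j, with H hours in every session:

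TEE_i − TEE_j = 1.11 × [(PAEE_i + RMR × H/24) − (PAEE_j + RMR × H/24)] = 1.11 × (PAEE_i − PAEE_j).

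RMR contributes 0 kcal whatever H is. On the kcal scale the test of condition on TEE is the test on PAEE multiplied by a constant.

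**Step 3, RMR counted to bedtime.** Each hour of bedtime difference moves TEE by 1.11 × RMR/24:

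- RMR 1400: 1.11 × 1400/24 = 64.75 kcal. A 100 kcal shift needs 100/64.75 = 1.54 h, or 93 min.
- RMR 2000: 1.11 × 2000/24 = 92.5 kcal. A 100 kcal shift needs 100/92.5 = 1.08 h, or 65 min.
- A wider RMR range of 1200 to 2200 gives 55.5 to 101.75 kcal per hour.

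**Step 4, illustrative power under Step 3 only.** The added SD of a paired difference is √2 × bedtime SD × kcal per hour. The smallest case is √2 × 0.5 × 64.75 = 45.8 kcal; the largest is √2 × 1.0 × 92.5 = 130.8 kcal. The table uses a paired t-test with n = 25 and a difference of 100 kcal.

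| SD of differences before bedtime noise | Power | With 45.8 kcal added | With 130.8 kcal added |
|---|---|---|---|
| 147.9 (gives the stated 90%) | 90.0% | SD 154.9, 87.2% | SD 197.5, 68.1% |
| 200 | 67.0% | SD 205.2, about 65% | SD 239.0, 51.9% |

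The 67% in the second row comes from how the SD of 200 is read in the sample-size statement. It is a separate matter and not a consequence of the RMR period.

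**Step 5, what remains under a fixed period.** The plan divides the mean difference by a pooled SD, and between-person spread in RMR enters that SD. With an assumed PAEE difference of 100 kcal and PAEE SD of 200, d on PAEE is 0.50. On TEE, d = 100/√(200² + s² + 2 × r × 200 × s), where s = RMR SD × H/24 and r is the correlation of PAEE with RMR; the factor 1.11 cancels. With RMR SD 200 kcal/day and r = 0:

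- 11 h: s = 91.7, d = 0.455
- 13 h: s = 108.3, d = 0.44
- 24 h: s = 200, d = 0.354

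Over RMR SDs of 100 to 300, periods of 11 or 24 h and r from 0 to 0.3, d runs from 0.49 down to 0.25. At r = −0.3 it runs from 0.52 to 0.33. This changes the description of the effect, not the test.

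**The case for a change.** The strongest contrary case is that the plan does not exclude counting RMR to bedtime. A post-exercise outcome followed to bedtime makes a matched window a natural reading, and a gap of little more than an hour would then equal the whole planning difference. The log transformation allowed under Statistical Analysis also breaks the cancellation, since a constant added before taking logs does not drop out. One sentence would settle the matter.

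Part of this stands. The period is indeed unstated, the kcal-per-hour arithmetic is right, and both Cohen's d and any log-scale analysis of TEE depend on the number of hours chosen.

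The inference to harm does not stand. In the text, bedtime qualifies accelerometer wear; nothing scales RMR by session. The power losses need that unstated reading together with an assumed RMR and an assumed bedtime SD. The planning SD is drawn from earlier crossover studies described as similar and is called conservative, so it may already contain bedtime variation, in which case the further loss is nil. Nor would settling the RMR period remove bedtime from the contrast: PAEE is itself accumulated until bedtime and varies with it on every reading. Finally, the Appendix figure is not available here, so what it shows about the measurement window cannot be held against the plan.

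**Conclusion.** No change is called for. With RMR measured once per participant, the sensible course is to count it over the same period in each session. RMR then contributes exactly 0 kcal to the condition contrasts, and P-values and power on the kcal scale are untouched. The same holds if PAEE alone is analysed.

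The shift of 65 to 93 kcal per hour of bedtime difference arises only if RMR is scaled to each session's bedtime, which the plan does not state, and it rests on an assumed RMR of 1400 to 2000 kcal/day. Even then it would be noise unless bedtime differed systematically by condition, in which case it would be bias. The fall in power from 90% to between 87% and 68% is illustrative only, because the documents give no bedtime variation and the planning SD may already include it.

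The remaining consequences are a descriptive Cohen's d on TEE that depends on the hours chosen, and the same dependence if TEE is log-transformed. A reader should bear both in mind when interpreting the results; neither is a fault in the planned comparison.
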